This prospective, multicentre, randomized, controlled, two parallel group, open-label trial based on pooled design was conducted across four tertiary care centres with study protocol approved by the institutional ethics committees of all participating centres: Adichunchanagiri Institute of Medical Sciences (AIMS), B. G. Nagara, JSS Medical College and Hospital (JSS), Mysore and Mysore Medical College and Research Institute (MMC&RI), Mysore and Rajarajeswari Medical College and Hospital (RRMCH), Bangalore, all centres in the state of Karnataka, India. The study was done under the supervision of primary investigator [name] N (AIMS) with the other principal investigators included [name], [name] and [name] M, respectively. The study protocol was approved by the institutional ethics committees of all participating centres and registered with ClinicalTrials.gov (Identifier: NCT07046403; Protocol Record Id: AIMS/IEC/206/2025). The investigators adhered to the applicable regulatory requirements and the trial was conducted in accordance with Good Clinical Practice guidelines and the Declaration of Helsinki. Written informed consent was obtained from all participants and patient confidentiality was rigorously maintained.

Patient screening and eligibility

The study population consisted of patients seeking treatment for DFUs. Eligible patients were those willing to participate and comply with scheduled visits on days 7, 14, 21, 28 (intervention period) and 35 (follow-up period). The study included two phases: screening and treatment. The screening phase aimed to determine patient eligibility for the treatment phase. During the screening, a series of assessments were conducted, including demographics, medical history, concomitant medications, vital signs, physical examination, foot ulcer history, clinical infection signs at the ulcer site, and ankle-brachial index measurement.

Inclusion criteria: Patients aged 18-75 years with type 1 or type 2 diabetes mellitus presenting with chronic foot ulcers were screened for eligibility. Target ulcer size between 5.0-20.0 cm² measured post-debridement; ulcer duration of 4-20 weeks; adequate circulation documented by ankle-brachial index (ABI) 0.7-1.3; and glycated haemoglobin (HbA1c) <12%.

Exclusion criteria included: Patients were excluded from the study if they met any of the following criteria: presence of active infection requiring systemic antibiotics, confirmed

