If the study ulcer was found to be 100% re-epithelialized during the visit, no further study procedures were conducted at that time. The patient was then scheduled for a follow-up visit after one week to confirm the healing. If complete healing was not observed, an assessment was performed to check for signs of clinical infection. If an infection was diagnosed, treatment with topical antimicrobials (betadine, chlorhexidine) or oral antibiotics was allowed, but the use of topical antibiotics (erythromycin, polymyxin, mupirocin) was prohibited.

Following the infection assessment, the ulcer was cleaned, photographed, and debrided at the investigator's discretion to ensure a clean, granulating ulcer base with minimal adherent slough. The SOC was then reapplied, and the patient was instructed to keep the bandaging dry. The patient was also advised to contact or visit the study site if the bandage became soiled or was removed. Topical antibiotics specifically on the wound were prohibited.

Systemic antibiotics were permitted when clinically needed.

Study completion

Patients completed the study four weeks after their first treatment visit. However, if a patient's study ulcer closed before the four-week mark, they were considered to have completed the study at that time. Complete healing of the study ulcer was defined as 100% re-epithelialization with no drainage. Throughout the treatment period, patients had the right to refuse participation or withdraw from the study at any time without prejudice. If a patient chose to withdraw from the study, their last recorded wound measurement was carried forward and used to calculate the change in wound size and their final outcome.

Outcome Measures

Primary Outcome:

1. Proportion of participants achieving wound size reduction at 4 weeks, measured using digital planimetry. Wound area was monitored at visits on days 7, 14, 21, 28 (intervention period) and 35 (follow-up period)

Secondary Outcomes:

1. Histological assessment of vascular incursion and wound biology was performed using punch biopsies (2mm diameter) obtained from the wound edge on day 5 post-treatment initiation. Histological parameters were evaluated using standardized scoring scales, including:

- a. vascular infiltration assessed on a 0-3 scale based on vessel count per high-power field,
- b. neo-epithelialization measured on a 0-3 scale based on epithelial migration distance from the wound edge,

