- c. fibroblast activity quantified on a 0-3 scale based on α -SMA positive fibroblast count and cellular morphology,
- d. capillary density measured as vessels per mm^2 using CD31 immunohistochemical staining,
- e. inflammatory response graded on a 0-3 semi-quantitative scale, and
- f. collagen deposition assessed on a 0-3 scale using Masson's Trichrome staining.

Additional secondary outcomes included

2. Time to complete wound closure defined as 100% re-epithelialization with no drainage,
3. Percentage wound area reduction measured weekly using standardized digital photography,
4. Mean number of treatment applications representing the total applications required per participant during the 4-week treatment period,
5. Adverse events including infection and other complications monitored throughout the study period,
6. Quality of life assessed using patient-reported visual analogue scale (VAS) measuring change from baseline to follow-up week, and
7. Scar quality evaluated using the Vancouver Scar Scale at 5 weeks post-treatment

Vascularity assessment was done using biopsy on day zero of application to be compared with day five after the application of HPTC or dHCAM. For histopathological assessment, before application and on the fifth day after the application of either HPTC or dHCAM, a 2 mm punch biopsy was obtained from the wound edge extending into the wound bed under local anaesthesia (2% lidocaine without epinephrine). Biopsy samples were immediately fixed in 10% neutral buffered formalin for 24 hours, processed through graded alcohol, and embedded in paraffin blocks. Serial sections of 4 μm thickness were prepared and stained with hematoxylin and eosin (H&E) for general morphology, Masson's trichrome for collagen assessment, CD31 immunohistochemistry for capillary density evaluation, and α -SMA immunohistochemistry for fibroblast activity. Histological parameters that were evaluated included vascular infiltration, neo-epithelialization, fibroblast activity, capillary density,

inflammatory response, and collagen deposition (Table 1). All histological assessments were performed by two independent pathologists blinded to treatment allocation. Inter-observer agreement was assessed using Cohen's kappa coefficient.

Table 1: Histological parameters evaluated in the ulcer bed at baseline and on day five of application

Parameter	Measurement tool	Criteria	Score

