Vascular infiltration	Assessed by counting new blood vessels (0–3 scale)	Minimal vascular ingrowth (<5 vessels/HPF)	0
		Mild infiltration (5–10 vessels/HPF)	1
		Moderate infiltration (11–20 vessels/HPF)	2
		Abundant infiltration (>20 vessels/HPF)	3
Neo-epithelialization	Measured as epithelial migration distance from wound edge (0–3 scale)	No epithelial migration	0
		Minimal migration (<25% wound coverage)	1
		Moderate migration (25–75% coverage)	2
		Extensive migration (>75% coverage)	3
Fibroblast activity	Quantified by counting α -SMA positive fibroblasts per HPF and assessment of fibroblast morphology (0–3 scale)	Sparse, inactive fibroblasts	0
		Moderate cellularity, minimal matrix production	1
		High cellularity, active-matrix synthesis	2
		Very high activity with extensive matrix deposition	3
Capillary density	Evaluated using CD31 staining, counted as vessels per mm^2 of tissue		
Inflammatory response	Graded semi-quantitatively (0–3 scale)	Minimal inflammatory infiltrate	0
		Mild chronic inflammation	1
		Moderate mixed inflammation	2
		Severe acute inflammation	3
Collagen deposition	Assessed using Masson's trichrome staining (0–3 scale)	Minimal collagen matrix	0
		Loose, immature collagen	1
		Moderate organized collagen	2
		Dense, mature collagen architecture	3

*Data presented as scoring criteria; all parameters assessed using standardized histological grading scales

Sample Size Calculation

Based on previous studies, we anticipated 85% of HPTC patients and 55% of dHACM patients would achieve wound reduction. With 80% power to detect a 25% absolute difference in complete wound closure at 5 weeks, 5% significance level, and assuming 10% dropout rate, a total of n=120 with 60 participants per group were required, pooled in from across 4 centres.

Statistical Analysis

Statistical analyses were performed using SPSS version 28.0 (IBM Corp, Armonk, NY, USA) and R version 4.3.0. Continuous variables were expressed as mean \pm standard deviation or median (interquartile range) based on normality testing using Shapiro-Wilk test. Categorical variables were presented as frequencies and percentages.

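### Neo-epithelialization is defined as a distance but scored as percent coverage on a 2 mm edge punch; the denominator is not stated, and if it is the ulcer, score 3 cannot be observed

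*Combined protocol and SAP*

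**What the plan says.** Outcome Measures, secondary outcome 1b, gives "neo-epithelialization measured on a 0-3 scale based on epithelial migration distance from the wound edge". The measurement-tool column of Table 1 says the same: "Measured as epithelial migration distance from wound edge (0–3 scale". No millimetre cut-offs are given.

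The criteria column of that Table 1 row uses a different quantity. Score 0 is no migration, score 1 is "Minimal migration (<25% wound coverage", score 2 is "Moderate migration (25–75% coverage" and score 3 is "Extensive migration (>75% coverage". Only the score 1 line says that it is the wound that is covered.

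The specimen is described twice in Outcome Measures: "punch biopsies (2mm diameter) obtained from the wound edge on day 5 post-treatment initiation" and "a 2 mm punch biopsy was obtained from the wound edge extending into the wound bed". Two blinded pathologists read it, at day 0 and day 5. The inclusion criteria set the ulcer size: "Target ulcer size between 5.0-20.0 cm² measured post-debridement".

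**The concern.** A distance and a share of area are different quantities, and the plan gives no rule for turning one into the other. A 2 mm specimen shows at most 2 mm of new epithelium, at one point on the margin. The eligible ulcers have circle-equivalent radii of roughly 13 to 25 mm. If the score means coverage of the ulcer, the upper categories may lie outside what the slide can show, and the same advance earns a different score in a small ulcer than in a large one. Randomization is stratified by site only, so a chance imbalance in ulcer size would carry into the score.

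The introduction puts particular weight on histology and expects superiority to come through better tissue regeneration. A row whose meaning each pathologist must supply weakens that argument, and it makes the planned kappa for this item hard to interpret.

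**Working it through.** The documents state no figure for the coverage visible in a punch, so there is nothing to reproduce. The check is geometric.

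**Inputs from the documents.** Ulcer area A from 5.0 to 20.0 cm² (inclusion criteria); punch 2 mm (Outcome Measures); cut-offs 25% and 75% (Table 1).

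**Assumptions, not in the documents.** Shape: a circle, then ellipses with length:width of 1.5, 2 and 3. Length d of the punch inside the original margin: 2 mm (most favourable) or 1 mm (punch centred on the edge). Epithelium advances equally all round.

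**Reading 1: coverage of the ulcer, circle.** With A in mm², r = √(A/π). Coverage from an advance d is 1 − (1 − d/r)². The advance needed for coverage f is r(1 − √(1 − f)), which is 0.134r for 25% and 0.5r for 75%.

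| A (cm²) | r (mm) | mm for 25% | mm for 75% | coverage, d = 2 mm | coverage, d = 1 mm |
|---|---|---|---|---|---|
| 5 | 12.62 | 1.69 | 6.31 | 29.2% | 15.2% |
| 7 | 14.93 | 2.00 | 7.46 | 25.0% | 12.9% |
| 10 | 17.84 | 2.39 | 8.92 | 21.2% | 10.9% |
| 20 | 25.23 | 3.38 | 12.62 | 15.2% | 7.8% |

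- Score 3: for 2 mm to equal 75%, r = 2/0.5 = 4 mm, so A = π × 16 ≈ 50 mm² = 0.50 cm². That is one tenth of the smallest eligible ulcer.
- Score 2 with d = 2 mm: r = 2/0.134 = 14.93 mm, so A ≈ 7.0 cm² is the largest ulcer in which it can be evidenced.
- Score 2 with d = 1 mm: the limit is 1.75 cm², below the eligible range.

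**Reading 1, ellipses.** Coverage = (perimeter × d − πd²)/A.

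| length:width | largest A for score 2, d = 2 mm | coverage at 5 cm², d = 2 mm | coverage at 5 cm², d = 1 mm |
|---|---|---|---|
| 1.5 | 7.5 cm² | 30.2% | 15.7% |
| 2 | 8.5 cm² | 32.1% | 16.7% |
| 3 | 11.1 cm² | 36.4% | 18.8% |

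The most favourable case reaches 36.4%, less than half of what score 3 requires. With d = 1 mm, score 2 is out of reach for every shape tried.

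**Dependence on size.** A 2 mm advance on a circle scores 2 at 5 cm² (29.2%) and 1 at 10 cm² (21.2%).

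**Reading 2: coverage of the section.** With the full 2 mm inside the margin, the cut-offs are 0.25 × 2 = 0.5 mm and 0.75 × 2 = 1.5 mm. A 1.6 mm tongue covers 1.6/2 = 80% and scores 3. On reading 1 the same slide gives 1 − (1 − 1.6/12.62)² = 24% at 5 cm², and less in larger ulcers, so on a circle it scores 1.

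**The case against.** The strongest reply is that the denominator is undefined rather than wrong. The word wound appears only in the score 1 line, and a pathologist with an edge section could reasonably grade the share of wound bed visible on it. All four scores could then occur. They could also occur if coverage came from planimetry. This stands: truncation is proven only on the ulcer reading. But the documents state neither alternative, and the score 1 wording points to the ulcer. The row needs correcting on any reading.

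A reader might go further and infer that the scale collapses to 0 and 1 for most patients. The documents do not support that. On a circle with 2 mm inside the margin, (20 − 7)/15 = 87% of the size interval is limited to scores 0 and 1, and this falls to 59% for a 3:1 ellipse. These are shares of the interval, not of patients, and no ulcer size distribution is given.

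Nor is the practical loss known, because the plan gives no expected day-5 coverage. With randomization and blinded readers, dependence on ulcer size adds noise and does not systematically favour an arm.

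Finally, a millimetre measure on the same punch is also capped at 2 mm or less. That is correct, and the fix has to allow for it.

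**Conclusion.** The concern holds in limited form. The scoring rule conflicts with its own definition and does not say coverage of what. On the ulcer reading, score 3 cannot be evidenced at any eligible size or any shape tried. Whether score 2 can be depends on ulcer size, ulcer shape and punch placement, none of which the plan ties to the score. On the section reading the categories work, but they mean something else, and one slide can move from score 1 to score 3.

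The definitional conflict rests on the text alone. The size limits rest on the assumed shape, placement and equal advance. The effect is confined to one of six histology parameters within one secondary outcome; the primary outcome is untouched.

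**What to change.** Replace the percent criteria in this row of Table 1 with epithelial tongue length in mm from the wound margin, measured blinded on the existing H&E sections. Report a tongue that spans the whole specimen as at or above the specimen limit (2 mm or less, depending on placement). Analyse the length as a continuous or rank-based variable. The Mann-Whitney test already in the plan handles values tied at the limit.

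If percent wound coverage is wanted, take it from the blinded day-5 planimetry. Data collection and follow-up lists day 5 as a visit, with planimetry at every visit, but the primary outcome's schedule of wound-area visits starts at day 7. Confirm first that day-5 areas were recorded.

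The cost is small if slides are unread: one table row, with the same slides and readers. The document is written in the past tense, so scoring may be complete. In that case the slides need a blinded re-measurement, and the change must be disclosed as a redefinition of the outcome. If that is not done, the report must state which denominator was used and must not describe the score as wound coverage.

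### The fibroblast activity score (outcome 1c) is defined by an α-SMA count and morphology, but its grades give no count bands and add a matrix judgement that overlaps with the collagen outcome (1f)

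*Combined protocol and SAP*

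**What the plan says.** Outcome Measures, Secondary Outcomes, item 1c reads "fibroblast activity quantified on a 0-3 scale based on" the α-SMA "positive fibroblast count and cellular morphology". The measurement-tool column of Table 1 gives the same two components: α-SMA "positive fibroblasts per HPF and assessment of fibroblast morphology". Neither place mentions matrix.

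The grades in Table 1 are:

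- 0: "Sparse, inactive fibroblasts"
- 1: "Moderate cellularity, minimal matrix production"
- 2: "High cellularity, active-matrix synthesis"
- 3: "Very high activity with extensive matrix deposition"

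The histology paragraph after the list of secondary outcomes names the stain as α-SMA "immunohistochemistry for fibroblast activity". It assigns H&E to morphology and Masson's trichrome to collagen, all on serial sections of the same biopsy, taken on day 0 and day 5. Collagen deposition is a separate 0-3 outcome (1f). Two pathologists read the slides independently and blind to arm, and their agreement is summarised by Cohen's kappa.

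**The concern.** The definition and the grades describe different things. A reader who has counted α-SMA positive cells finds no rule for turning the count into a grade, and must also judge matrix, which the definition never asked for.

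What is at stake is interpretation. The Introduction expects HPTC to do better because of heightened cell activity and improved regeneration, and criticises earlier comparative work for lacking histology that explains mechanism. Outcome 1c is the fibroblast evidence for that account. If its grade depends partly on matrix, a difference in 1c cannot be attributed to fibroblasts alone. Agreement between 1c and 1f would also be partly built in, and should not be read as two separate confirmations.

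**Working it through.** The documents state no figure for this outcome, so the main check is to read the grades against the definition.

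**Step 1: content of each grade.**

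| Grade | Count band | Word for cell number | Matrix named |
|---|---|---|---|
| 0 | no | yes (sparse) | no |
| 1 | no | yes (moderate) | yes |
| 2 | no | yes (high) | yes |
| 3 | no | no | yes |
| Total | 0 of 4 | 3 of 4 | 3 of 4 |

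**Step 2: comparison within the same table.** Vascular infiltration is also scored by counting, and its grades have explicit bands: <5, 5–10, 11–20 and >20 vessels per HPF. The fibroblast row announces a count and supplies no equivalent.

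**Step 3: discordant biopsies.** Cross the three cell-number words (sparse, moderate, high) with the three matrix levels (minimal, active, extensive). That gives 3 × 3 = 9 pairings.

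- Two are written out as grades: moderate/minimal (1) and high/active (2).
- Three have sparse cells. They could go to grade 0, which is silent on matrix, provided the cells are inactive.
- One, high/extensive, could reasonably be read as grade 3.
- Three match no grade: moderate/active, moderate/extensive and high/minimal.

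Check: 2 + 3 + 1 + 3 = 9. For the last three the reader must decide whether cells or matrix takes precedence, and no rule is given. Kappa would show whether the two readers decide alike; it would not show whether the grade follows the count.

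**Step 4: sensitivity of a between-arm test, under assumptions only.** Assume equal true fibroblast activity, grades 0–3 at 20/40/30/10%, 60 per arm, and a two-sided Mann-Whitney test at 0.05. Raise a share q of the grades in one arm by one step (capped at 3). With 20,000 simulated trials per setting:

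| q, one arm only | Rejection rate |
|---|---|
| 0 | 5% |
| 0.02 | 5% |
| 0.05 | 6% |
| 0.10 | 8% |
| 0.20 | 18% |
| 0.30 | 34% |
| 0.40 | 54% |

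With 60 × 0.9 = 54 per arm, to allow for the planned 10% dropout, q = 0.10 to 0.40 gives 8%, 16%, 31% and 50%. If both arms are shifted by the same q, the rate stays at 5%. The grade distribution, q and the one-sided shift are all assumed, because the documents give none of them. The table shows what unequal matrix grading could do. It does not estimate what it does in this trial.

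**The case against.** Three stronger readings are tempting, and the documents do not support them.

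**That the count is unused, so the score fails to measure what it claims.** The definition has two components, count and morphology, and grades 0 to 2 use ordered words for cell number. The count may well guide the grade informally. Matrix production and synthesis in grades 1 and 2 could also be defended as a description of what the cells are doing, and so as part of morphology. This objection stands: the fault is a missing rule and a mixed construct, not a count shown to be ignored. It helps less with grade 3, which has no cell-number word and refers to deposited matrix.

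**That matrix cannot be judged because the assigned stain is α-SMA.** The documents do not say what α-SMA can or cannot show, and H&E and trichrome sections of the same biopsy were available. The remaining gap is that the plan does not say which section informs the matrix part of the grade.

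**That the grading favours HPTC because its collagen sheet could be read as matrix.** Nothing in the documents says the sheet is present in a day-5 section or would be mistaken for tissue. The Introduction says that dHACM carries extracellular matrix constituents too, so even the direction of any bias is open. Blinded reading excludes knowing bias, although it does not make the scale valid.

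It is also fair to say that count bands and a named stain would repair the grade without replacing it, and that replacing it by the count alone would drop the morphology component.

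**Conclusion.** The point holds as a specification fault. No grade carries a count band (0 of 4), three of four grades require a matrix judgement outside the definition, and three of nine cell-by-matrix pairings have no grade. As written, 1c mixes cell number with matrix, overlaps with 1f, and is weak separate evidence for a cellular mechanism. This rests on the wording alone and needs no outside knowledge of the stains.

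The direction and size of any between-arm bias cannot be determined from the documents. The simulated rates are conditional on assumed inputs and should not be quoted as the trial's false-positive rate.

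The weight is minor: one of six parameters in a secondary histological outcome. The primary outcome and sample size are unaffected.

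**What to change.** Analyse 1c as the α-SMA positive fibroblast count per HPF, averaged over a stated fixed number of fields, comparing arms at day 5 with adjustment for the day-0 count. If the 0-3 grade is kept, define each level by a count band and fibroblast morphology, remove the matrix wording, and assess matrix only under 1f.

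The protocol is written in the past tense, so grading may be complete. In that case leave the grades as they are, report the counts beside them labelled as a later addition, and state that the grade includes a matrix judgement. This depends on the counts having been recorded as data and not used only to assign a grade, which the documents do not settle.

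The cost is an edit to one row of Table 1, matching wording in item 1c and one line in Statistical Analysis. The downsides are that the count is not on the 0-3 scale shared by most of the other histology scores, and that morphology is then carried only by the retained grade.

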Between-group comparisons for continuous variables used independent t-tests or Mann-Whitney U tests. Chi-square or Fisher's exact tests were employed for categorical variables. Time-to-event analysis used Kaplan-Meier curves with log-rank tests. Mixed-effects models analysed repeated measures data. All analyses followed the intention-to-treat principle, with sensitivity analyses using per-protocol populations. A two-sided p-value of less than 0.05 was considered statistically significant for all analyses, with p-values less than 0.001 indicating highly significant differences between groups.

Data collection and follow-up

Demographic data, medical history, comorbidities, and baseline wound characteristics were recorded. Laboratory parameters, including haemoglobin, albumin, and glycated haemoglobin (HbA1c), were obtained at baseline and follow-up visits.

Patients were evaluated at baseline, day 5, day 7, day 14, day 21, day 28, and day 35. At each visit, wound measurements were performed using standardized digital planimetry, with wound area calculated in cm^2 . Histopathology examination results were recorded on baseline day 0 and day 5 after application. Digital photographs were taken for documentation and independent assessment. Complete wound closure was defined as 100% epithelialization without drainage or dressing requirements. Any adverse events, if they occurred, were duly noted and notified. Scar quality and durability were assessed at each visit, with patient satisfaction assessed at the fifth week, during the one-week follow-up.

Ethical Considerations

The study was conducted in accordance with ethical principles outlined in the Declaration of Helsinki. Written informed consent was obtained from all participants before enrolment.

Participant confidentiality was maintained throughout the study period. Data safety monitoring was performed by an independent committee.

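### The 80% power claim is for complete closure at 5 weeks, not for the declared primary outcome of wound size reduction at 4 weeks, and no closure rates are given to check it

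*Combined protocol and SAP*

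**What the plan says.** The Outcome Measures section declares one primary outcome: "Proportion of participants achieving wound size reduction at 4 weeks, measured using digital planimetry". It gives no threshold for how much reduction counts. Closure is listed among the secondary outcomes, as a time-to-event measure: "Time to complete wound closure defined as 100% re-epithelialization with no drainage". A proportion closed at 5 weeks is not a listed outcome.

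The Sample Size Calculation section first gives anticipated rates for wound reduction: "we anticipated 85% of HPTC patients and 55% of dHACM patients would achieve wound reduction". It then states power for something else: "With 80% power to detect a 25% absolute difference in complete wound closure at 5 weeks". The remaining inputs are "5% significance level, and assuming 10% dropout rate", leading to 60 per group and 120 in total.

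Two further statements affect how many participants enter the primary test. Under Study completion, for a participant who withdraws, "their last recorded wound measurement was carried forward and used to calculate the change in wound size and their final outcome". Under Statistical Analysis, "All analyses followed the intention-to-treat principle, with sensitivity analyses using per-protocol populations".

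On timing, Study completion says "Patients completed the study four weeks after their first treatment visit", while the visit schedule includes a follow-up visit on day 35.

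**The concern.** The power statement differs from the primary outcome in three ways:

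- **Endpoint:** closure instead of size reduction.
- **Time:** 5 weeks instead of 4.
- **Effect:** 25 points instead of the 30 implied by 85% and 55%.

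The endpoints are not interchangeable. The plan defines closure separately, as full re-epithelialization without drainage, and a wound can shrink a great deal without meeting that definition.

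The power of a two-proportion comparison depends on both rates, not only on their difference. With no closure rate in either arm, a 25-point closure difference has no base rate, so the 80% cannot be checked.

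The sample-size paragraph is where a reader looks to see which endpoint the trial was built to test. If it names a different endpoint at a different time, the reader cannot tell which comparison was meant to be decisive, and the primary result is open to a charge of endpoint switching.

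**Working it through.** **Inputs.** From Sample Size Calculation: 85% and 55% (wound reduction), 25 points (closure), 80% power, 5% level, 10% dropout, 60 per group. From Statistical Analysis: two-sided testing, with chi-square or Fisher's exact test for categorical variables. From Randomization and Blinding: 1:1 allocation. Closure rates are not given, so they are assumed over a range below.

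**Formulas** (pooled variance, two-sided 5%, no continuity correction), with d = p1 − p2, p̄ the mean of p1 and p2, and q = 1 − p:

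- n per arm = [1.96·√(2p̄q̄) + 0.8416·√(p1q1 + p2q2)]² / d², then divided by 0.9 for dropout
- power with m per arm = Φ{[d·√m − 1.96·√(2p̄q̄)] / √(p1q1 + p2q2)}

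**Step 1: reproduce the plan's figure.** Take the 55% dHACM rate and add 25 points (80% against 55%):

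- n = [1.96·0.6624 + 0.8416·0.6384]² / 0.0625 = 53.9, so 54
- 54 / 0.9 = 60 per arm, 120 in total

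This matches. But it places a closure difference on a wound-reduction rate and implies an 80% HPTC rate that appears nowhere in the document.

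**Step 2: is that derivation unique?** No. The pair 45% against 20% has the same variance terms and the same difference, so it also gives 53.9, then 54, then 60. The stated sample size does not reveal which rates were used. Keeping the 85% and subtracting 25 points (85% against 60%) gives 48.9, so 49; 49 / 0.9 = 54.4, so 55, which does not match.

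**Step 3: the declared primary outcome at its stated rates (85% against 55%).**

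- n = [1.96·0.6481 + 0.8416·0.6124]² / 0.09 = 35.4, so 36; 36 / 0.9 = 40 per arm, 80 in total
- power with 54 per arm: Φ[(0.30·7.348 − 1.270) / 0.6124] = Φ(1.526) = 93.6%
- power with 60 per arm: Φ[(0.30·7.746 − 1.270) / 0.6124] = Φ(1.720) = 95.7%

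The 54 applies if 10% are lost. The 60 applies if withdrawals stay in by carry-forward under intention to treat, before any dilution from the carried-forward values. Exact calculation gives 93.9% and 96.2% for chi-square, and 91.0% and 93.8% for Fisher's exact test.

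**Step 4: the endpoint the statement names (25-point closure gap, assumed control rates).**

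| Control vs HPTC closure rate | Power, 54 per arm | Power, 60 per arm |
|---|---|---|
| 5% vs 30% | 93.9% | 95.9% |
| 20% vs 45% | 80.1% | 84.1% |
| 25% vs 50% | 77.3% | 81.6% |
| 37.5% vs 62.5% (minimum) | 74.5% | 78.9% |
| 55% vs 80% | 80.1% | 84.1% |
| 65% vs 90% | 88.6% | 91.7% |
| 70% vs 95% | 93.9% | 95.9% |

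By this formula, power is below 80% for control rates between about 20% and 55% with 54 per arm, and between about 30% and 45% with 60 per arm. In the latter case the shortfall is about 1 point at most. Fisher's exact test has less power: at 37.5% against 62.5% it gives 66.0% with 54 per arm and 74.7% with 60.

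**The case against.** The strongest reply is that nothing is miscalculated. The 55% rate stands in the sentence just before the 25-point target, and together they return exactly 60 per arm. The simplest reading is a deliberately cautious target, 25 points where 30 were expected, with the endpoint mislabelled. The pair 45% against 20% is only the mirror image of 80% against 55%, and 20% has no source in the document. Five weeks also has some basis: there is a day-35 visit, and healing is to be confirmed one week after it is seen, so closure status at 5 weeks could be derived. The trial is described in the past tense, so a correction changes no recruitment decision.

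Much of this stands. The sample size is sound, the primary test is not shown to be underpowered, and the cautious-target reading is plausible. Power for the closure endpoint is bounded rather than wholly unknown: if the true gap is 25 points, the formula never falls below about 74.5% with 54 per arm.

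It does not cure the mismatch. The document does not say that 25 points was a reduced target, and a reduced target would not explain the change of endpoint and week. A day-35 visit does not make closure at that visit the primary outcome. The mirror-image pair is not offered as a rival derivation; it shows only that matching 120 does not identify the rates.

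**Conclusion.** The concern holds and the statement needs correcting. The 80% is not the power of the declared primary comparison, which at 85% and 55% is about 94% with 54 per arm and 96% with 60 (91% and 94% with Fisher's exact test). For closure at 5 weeks no unique power follows; over assumed control rates of 5% to 70% it is 74.5% to 93.9% with 54 per arm and 78.9% to 95.9% with 60.

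The harm is a power claim that is wrong as written for the primary outcome, not a trial that is too small. The primary-outcome figures assume that the 85% and 55% use the same definition of wound size reduction as the primary analysis, which the document does not establish. The closure figures rest on control rates assumed here and on a true difference of 25 points.

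**What to change.** Keep 120 participants and the primary outcome as declared, and issue a dated correction of the sample-size paragraph. The sponsor should first retrieve the original calculation, and then:

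1. State power for the primary outcome. For example: at anticipated rates of 85% (HPTC) and 55% (dHACM) for wound size reduction at 4 weeks, 60 per arm gives about 94% power with 54 evaluable per arm and about 96% if all 60 are analysed with carry-forward (two-sided 5%). Name the test; if it is Fisher's exact, the figures are about 91% and 94%. Mark these figures as computed for the correction, so that they are not read as the original rationale.
2. State the definition of wound size reduction, including any threshold, and confirm that the 85% and 55% use it. The sentence in item 1 depends on this.
3. If 25 points was a deliberately smaller target, say so and give the pair of rates originally used, taken from the original calculation and not chosen because it returns 120.
4. Remove closure at 5 weeks from the power statement. If the original calculation did use closure, disclose that as a discrepancy and report its closure rates, without changing the primary outcome.

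The cost is one corrected paragraph and a search of the sponsor's records. The sample size, primary outcome, visits and analysis do not change.
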